The primary outcome variable for the first objective will be topics and features (derived using the Latent Dirichlet Allocation [LDA] method for clustering language data) as well as a model-based approach of latent class analysis (LCA). We hypothesize: H1: There will be a difference in themes and topics posted by patients with heart disease and for patients without heart disease and use and engagement

phenotypes reflecting quantity, quality, and interaction of posts will be associated with health status, social media perceptions, and patient activation. The second objective outcome variable will be any CHD event. We hypothesize: H2: Adding digital data variables to conventionally-derived predictive models will improve the AUC for forecasting/predicting a CHD related event in a patient. The third objective outcome measure will be health care utilization measured by cost. We hypothesize: H3: Unique digital data variables identified for patients with heart disease and without heart disease will better predict future health care utilization costs for the health system. The fourth objective outcome measure will be the impact of dynamic health events on CV health behaviors. We have the following three hypotheses: H4,1: Digital media data will provide valid measures of health behaviors when compared with traditional sources. H4,2: Variations in digital data about modifiable CV health behaviors will correlate with dynamic health events. H4,3: Modifiable CV health behaviors (smoking, poor diet, and reduced physical activity) will increase more in response to dynamic health events in low income and minority communities.

Secondary outcome variable(s)

Given the correlational nature of this research the distinction between primary and secondary outcome variables is not particularly apparent.

Background

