
some patients and not others. As the dependent variable will be cost, we will be attentive to informative censoring and right skewness, potentially using generalized linear models under a gamma distribution and log link. To account for informative censoring we will use inverse probability of censoring weighting. We will also explore the application of our new nested g-computation approach that allows for informative censoring and time- varying covariates to obtain future cost predictions. Additionally, we will generate summary statistics to describe the cohort and survey responses. We will use the model-based approach of latent class analysis (LCA)- to classify individuals into previously unmeasured subgroups. Variables to include in the LCA will include: demographics, years of platform use, posting: volume, quality, retransmission, and engagement. We will use the Bayesian information criterion to assess goodness of model fit, entropy to assess variations between classes, and the parametric bootstrapped likelihood ratio test to assess if a model with  $k$  classes has better performance than  $k-1$  classes. We will then use a regression model to compare with measures of health status, social media perceptions, and readiness/activation for each latent class. Models will be adjusted for demographics.

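### The engagement-class regression for H1 makes no allowance for classification error, so its class contrasts can be biased and its intervals too narrow unless the classes are well separated

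*SAP*

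**What the plan says.** The LCA text stands near the end of the SAP's Final Analysis Plan, and the same text appears in the Protocol under Analysis Plan. It has two stages.

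- Stage 1: the LCA is used "to classify individuals into previously unmeasured subgroups". Fit is judged by BIC, the number of classes by "the parametric bootstrapped likelihood ratio test to assess if a model with" k classes improves on k-1, and the plan adds "entropy to assess variations between classes".
- Stage 2: "We will then use a regression model to compare with measures of health status, social media perceptions, and readiness/activation for each latent class", followed by "Models will be adjusted for demographics".

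The indicators are listed as: "Variables to include in the LCA will include: demographics, years of platform use, posting: volume, quality, retransmission, and engagement". Demographics are therefore used in both stages.

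The analysis serves the second half of H1 (Protocol, Primary outcome variable(s)), under which "phenotypes reflecting quantity, quality, and interaction of posts will be associated with health status, social media perceptions, and patient activation". No other analysis is given for that part of H1.

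The assignment rule is not stated. There is no mention of posterior weighting, pseudo-class draws, a bias-adjusted three-step method or a one-step model. The imputation and back-off methods elsewhere in the SAP deal with unequal amounts of data across modalities, not with uncertain class membership.

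**The concern.** A latent class is inferred from indicators, so some people end up in the wrong class. Each assigned group is then a mixture of true classes, and a regression on assigned class compares mixtures. With two classes and error unrelated to the outcome, this pulls the group means together. The bias does not shrink as n grows while the standard error does, so coverage worsens with a larger sample.

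Entropy is the statistic that tells how certain the classification is. The plan computes it but describes it as a measure of differences between classes, sets no minimum, and gives it no consequence for the regression. At stake are the size and the intervals of every phenotype association reported under H1.

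**Working it through.** **Inputs.** The documents give no entropy, number of classes, class sizes, effect size, alpha or power for this step, and no figure to reproduce. The study target is 1000 (Protocol, Study duration). The extra survey that supplies the outcomes is optional, and additional Objective 1 participants come from registries, so the n for this regression is unknown. Everything else below is assumed: outcome SD 1, two-sided 5%, and a range of entropies.

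**Formulas for two classes.** For equal classes with misclassification rate e, expected contrast = true gap × (1 − 2e). This is used here only as a rough check for a 40/60 split. Approximate coverage with bias b is Φ(1.96 − b/se) − Φ(−1.96 − b/se). With n=1000 split 40/60, se = √(1/400 + 1/600) = 0.0645.

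**Two classes, parameters estimated.** Split 40/60, six binary indicators, class model fitted by EM, n=1000, true gap 0.5 SD, 300 replicates. Assigned class means modal class followed by ordinary least squares. Corrected means BCH three-step with sandwich standard errors.

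| Entropy | e | 1 − 2e | Assigned: estimate (ratio) | Assigned: coverage, simulated (formula) | Corrected: estimate | Corrected: coverage |
|---|---|---|---|---|---|---|
| 0.98 | 0.007 | 0.986 | 0.496 (0.99) | 97% (95%) | 0.502 | 97% |
| 0.82 | 0.052 | 0.896 | 0.452 (0.90) | 90% (88%) | 0.499 | 97% |
| 0.69 | 0.093 | 0.814 | 0.408 (0.82) | 71% (70%) | 0.494 | 91% |
| 0.53 | 0.151 | 0.698 | 0.348 (0.70) | 36% (35%) | 0.488 | 93% |

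For the last row: b = 0.5 − 0.348 = 0.152; b/se = 2.36; Φ(1.96 − 2.36) ≈ 0.35. Monte Carlo error on coverage is about 1 point near 95% and about 3 points at the lowest value.

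The same runs with a true gap of 0.3 SD gave assigned-class coverage of 95%, 91%, 89% and 71%. With a true gap of 0 there was no bias, and type I error was 4-6%.

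**Second two-class check, parameters known.** Split 40/60, 0.5 SD, n=1000. At entropy 0.96, 0.77 and 0.62 the assigned-class estimates were 0.49, 0.44 and 0.39, that is, bias of 2%, 12% and 22%. Coverage was 96%, 87% and 60%. BCH gave 0.50 with 95-96%.

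**Effect of n.** Two equal classes, four Gaussian indicators, entropy 0.55, 0.5 SD: coverage was 68-69% at n=500 and 43-44% at n=1000, over two separate sets of runs.

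**Three ordered classes.** Eight binary indicators, n=1000, entropy 0.64, 18-19% misclassified. Coverage here carries an error of up to about 4-5 points.

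- A true middle-versus-low contrast of 0 was estimated as 0.06 with 88% coverage, so it moved away from zero (about 12% false rejections).
- A true 0.5 was estimated as 0.31-0.37 for middle versus low (coverage 27-58%) and as 0.42-0.43 for high versus low (84-88%).

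**Demographics in both stages.** With one binary demographic strongly tied to class (80% against 20%) used as indicator and covariate, true gap 0.5 SD and n=1000, standard BCH overshot: 0.59-0.60 at entropy 0.71 (coverage 89-91%) and about 0.56 at 0.82 (92-93%). With a weaker link (65% against 35%) it was unbiased. Standard BCH assumes that classification error does not depend on the covariates, which fails here.

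**Power.** With an 80/20 split, 0.5 SD, n=500 and entropy 0.52, power was 61% for assigned class, 59% for BCH and 99.5% with the true classes. Check of the last figure: se = √(1/100 + 1/400) = 0.112; 0.5/0.112 = 4.47; Φ(4.47 − 1.96) = 99.4%.

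**The case against.** The strongest reply is that the plan is under-specified rather than wrong. A reader might infer that class will be entered as an error-free variable. The text does not say so: it never states modal assignment, and a weighted or corrected analysis is not excluded. That stands, and the secure finding is that the method is unstated. Ordinary assignment is still the natural reading of a plan that classifies and then regresses, particularly as the SAP does name its corrections elsewhere (robust variance for the Cox models, censoring weights for cost).

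Other stronger readings also go too far.

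- That associations are always understated. This is assured only for two classes with error unrelated to the outcome. The plan leaves the number of classes to the data, and with three classes a null contrast moved away from zero.
- That the harm is certain and large. At entropy near 0.98 it is negligible, and coverage below 50% needs low entropy together with a large n that may not be reached.
- That the correction wins back power. It does not; the loss comes from uncertain classes.
- That off-the-shelf BCH suffices. With demographics in both stages it can overshoot.

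It is also fair that the Protocol (Secondary outcome variable(s)) describes the research as correlational, without a clear ranking of outcomes, and that the two-class error creates no false positives. This limits the consequence but does not remove it, because this regression is the only analysis offered for the phenotype part of H1.

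**Conclusion.** The concern holds in conditional form. The plan has no stated allowance for classification error. If class is assigned in the ordinary way, contrasts are biased and intervals under-cover unless separation is high. For two classes, 0.5 SD and n=1000, the range is:

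- entropy 0.96-0.98: bias about 1-3%, coverage near nominal;
- entropy about 0.8: bias about 10-12%, coverage 87-90%;
- entropy about 0.5-0.6: bias about 20-30%, coverage 36-60%.

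Which row applies cannot be known from the documents. All figures rest on assumed indicators, class sizes and effect sizes. The mechanism itself appeared with binary and Gaussian indicators, and with class parameters both estimated and known. It is worth settling before the classes are fitted.

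**What to change.** Keep the LCA and the rules for choosing the number of classes. Then amend the SAP as follows.

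1. State how class membership enters the regression. Make a classification-error-corrected analysis primary: BCH or maximum-likelihood three-step with robust standard errors, or a one-step model.
2. Show the assigned-class regression as a sensitivity analysis.
3. Report entropy and the average posterior probability per class, described as classification certainty.
4. Give each demographic variable one role, indicator or covariate. Otherwise use a one-step model, or a correction that lets classification error depend on the covariate.

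The cost is SAP wording and a software option; no new data are needed. Confidence intervals become wider. In the two-class case the corrected contrast is roughly the assigned-class contrast divided by the attenuation ratio, and its standard error scales alike. The widening is therefore about 1/0.99 = 1.01 times at entropy 0.98 and 1/0.90 = 1.11 at 0.82, which is slight, but about 1/0.70 = 1.43 at 0.53. That width reflects the real uncertainty about class, and the report should not present the correction as a gain in power.
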